TITLE: UPPER ARM VS. FOREARM PLACEMENT OF EXTENDED DWELL CATHETERS: A COMPARATIVE EVALUATION OF BLOOD SAMPLING AND FUNCTIONALITY

NCT04409418

Approval date: 07/12/2022

Study Protocol and Statistical Analysis Plan

UPPER ARM VS. FOREARM PLACEMENT OF EXTENDED DWELL CATHETERS: A COMPARATIVE EVALUATION OF BLOOD SAMPLING AND FUNCTIONALITY

Background:

Nearly all hospitalized patients require intravenous (IV) access for treatment. Patients rely on functional vascular access to receive life saving IV therapies. Generally, peripheral IVs have high failure rates with 19-25% of IVs failing prior to completion of therapy and 45-56% of ultrasound-guided peripheral IVs failing prior to completion of therapy. Dislodgment, infiltration/extravasation, and phlebitis are common complications that lead to early failure. ¹⁻⁵

Many patients require ongoing blood draws or phlebotomy for laboratory testing during hospitalization. Hospitals generally avoid phlebotomy from peripheral IV catheters because they have been associated with increased rates of inaccurate laboratory testing and can increase dislodgment, infiltration, and phlebitis complications.⁶ Patients are subjected to multiple needlesticks for blood sampling causing patient dissatisfaction and anxiety.⁷ Further, health care workers are exposed to blood borne pathogens as blood draws can cause needlestick injuries.⁸

Extended dwell catheters (EDC) offer a viable alternative to peripheral IVs, especially for patients with prolonged hospital stays. EDCs are peripheral venous access devices placed under ultrasound guidance that are most commonly placed in the basilica, brachial, or cephalic veins and can be inserted above or below the antecubital fossa. These catheters can be left in place for up to 30 days and have an improved survival profile when compared to peripheral IVs.^{9.10} While there is limited evidence on blood draw ability from these catheters, EDCs can be accessed for routine blood draws and potentially eliminate the need for additional needlesticks.

There is very limited research evaluating the impact of IV placement site on functionality or blood sampling ability. Only one small study of ultrasound-guided IV placements evaluated site in a prospective comparative fashion. The comparison was limited to evaluation of 56 patients in the "distal" or forearm group which comprised insertions in the antecubital/forearm area and 95 patients in the upper arm site. The authors concluded that "distal" placements have improved survival.¹¹ Further research is necessary to draw conclusions about EDCs and functionality/blood draws.

The potential value of forearm placements is especially relevant for patients with renal insufficiency. In the past three decades, there has been a significant increase in the patient population with chronic kidney disease. As the renal disease may progress and patients may require dialysis and establishment of an arteriovenous fistula, it is necessary to preserve the vasculature of the upper arm.¹²

UPPER ARM VS. FOREARM PLACEMENT OF EXTENDED DWELL CATHETERS: A COMPARATIVE EVALUATION OF BLOOD SAMPLING AND FUNCTIONALITY

In summary, there is a gap of knowledge on EDCs and blood draw ability regardless of site of insertion. While survival of EDCs has been evaluated, there is no literature that compares survival of upper arm to lower arm placement.

Hypothesis/Objectives:

We hypothesize the forearm is the favorable site for ultrasound-guided IV establishment in terms of survival. Placement of the catheter in the forearm to avoid antecubital fossa or muscle bellies of the upper arm reduces kinking and involves insertion in more shallow vessels and likely enhances survival of the catheter.

We hypothesize the forearm provides similar blood sampling functionality compared to upper arm insertion.

We aim to quantify the difference in blood draw ability and catheter survival, comparing placement of an extended dwell catheter in the upper arm to the forearm.

Specific Aims:

Specific Aim 1: To compare upper arm versus forearm extended dwell catheter placement for blood sampling functionality.

For Aim 1, blood sampling ability of the forearm compared to upper arm will be evaluated by daily blood draws prior to patient discharge. The event is failure to aspirate blood during follow-up assessment during hospitalization.

Specific Aim 2: To compare upper arm versus forearm extended dwell catheter placement for dwell time/survival of catheter.

For Aim 2, an improved survival of the forearm placed catheter will be evaluated by functionality of catheter for intravenous therapy prior to patient discharge. The event is failure of functionality identified as inability to infuse without resistance during follow-up assessment during hospitalization. Duration of dwell and functional failure of the catheter will be employed to estimate catheter survival.

Specific Aim 3: To compare upper arm versus forearm extended dwell catheter placement for symptomatic catheter-related upper extremity venous thrombosis (CR-UEVT).

For Aim 3, we will measure incidence of all symptomatic CR-UEVT inclusive of superficial thrombophlebitis (SVT) and deep venous thrombosis (DVT) confirmed

UPPER ARM VS. FOREARM PLACEMENT OF EXTENDED DWELL CATHETERS: A COMPARATIVE EVALUATION OF BLOOD SAMPLING AND FUNCTIONALITY

by upper extremity venous duplex evaluation, to assess for a difference in thrombosis when an EDC is placed in the forearm compared to the upper arm.

Study Design

We propose a single-site, prospective two-arm randomized investigation of blood sampling and catheter survival of extended dwell catheters when site selection is evaluated. Specifically, EDC insertions in the forearm will be compared to upper arm insertions. The primary objective of this study is to demonstrate that blood sampling of the forearm (experimental group) is not inferior to blood sampling of the upper arm (control group). Exploratory secondary and adjusted multivariable analyses will also be conducted.

A single lumen, 20 gauge 8 cm EDC (BARD Powerglide STTM Midline Catheter) will be utilized for this evaluation.

We aim to recruit 96 patients with 48 in each arm to assess blood sampling functionality.

Study Population and Eligibility:

A cohort of clinicians are proficient in ultrasound-guided vascular access at our hospital. In the emergency department (ED), several physicians and nurses are competent in the procedure. On the inpatient side, the Vascular Access Team (VAT) at our hospital receives daily consults for patients that have advanced vascular access needs. This includes patients with prolonged vascular access needs and/or difficult vascular access patients. All inserters are trained to place a number of catheters with ultrasound-guidance: peripheral IVs, midlines, and EDCs.

Eligible inpatient participants include: 1. Consult to VAT for vascular access device placement 2. Patient requires peripheral access. 3.18 years and older. Eligible ED patients include 1. 18 years and older 2. Difficult vascular access and anticipated hospital admission. Difficult vascular access is defined as: 1. Patient with no visible veins (>2 mm) or palpable veins in the upper extremity. Patients will be excluded if: 1. Multiple lumens required 2. Existing functional vascular access device proximal to the targeted area of insertion. This does not include superficial non-ultrasound guided peripheral IVs. 3. Upper extremity cannot be accessed due to a coexisting medical condition. 4. Cognitively impaired.

Patients meeting inclusion criteria will be consented and randomized by research staff to either upper arm or forearm insertion. If the inserter has no adequate target visualized in the randomly selected site, the inserter may evaluate another site that

UPPER ARM VS. FOREARM PLACEMENT OF EXTENDED DWELL CATHETERS: A COMPARATIVE EVALUATION OF BLOOD SAMPLING AND FUNCTIONALITY

is more suitable for cannulation. The site of insertion will be recorded and pertinent information will be collected similar to other enrollments.

Practitioner Participation/Training

Advanced Practice Providers (APP) within the VAT and ED practitioners proficient in ultrasound-guided vascular access at the Royal Oak campus are eligible to place catheters for this study. Participation in this study is not required and will be carried out on a strictly voluntary basis. Providers have limited experience with the BARD Powerglide STTM Midline. The clinical team from BARD will be expected to develop an educational/training pathway for providers to achieve proficiency prior to subject recruitment. A possible training/credentialing pathway may consist of: 1 hour didactic training followed by phantom training on a vein block +/- insertions on real patients. Once trained, providers can train the other providers.

Initial Assessment

Post-consent, eligible patients will be randomly allocated to the experimental group (forearm) or the control group (upper arm) in a ratio of 1:1 via a computergenerated randomization schedule. Research staff at the Department of Biostatistics will perform concealed immediate assignment by following a block scheme. Sealed envelopes containing the randomized IV access arm will be revealed at the bedside.

After patient enrollment, the inserter is engaged to perform the procedure. Only providers that are credentialed in ultrasound-guided vascular access will place catheters in study subjects. The research team will capture and save images of vessel depth and vessel diameter in short axis using the Sonosite or Mindray ultrasound equipment. Ultrasound guidance will be used for the initial assessment and procedure. The high frequency linear array transducer will be used for all procedures. Inserters will evaluate the vessel for valves, thrombosis, trajectory, and collapsibility per routine care. If the vein is appropriate for cannulation, the practitioner will continue with the procedure. Post-cannulation and post securement, functionality is confirmed with blood sampling (10 cc) and flush without resistance. A neutral pressure needle-free IV connector (One-link by Baxter Medical) will be connected to all lines. If the patient is randomized to the control group, the research staff will direct the inserter to choose either the basilic, cephalic or brachial vein at least 2 cm above the antecubital fossa. If the patient is randomized to the experimental group, the research staff will direct the inserter to place the catheter into the forearm at least 10 cm away from the antecubital fossa to ensure the distal tip of the catheter does not terminate in the antecubital fossa. The cephalic and basilic veins are typically cannulated in the forearm. If no adequate target is visualized in the randomly selected site, the inserter may evaluate another

UPPER ARM VS. FOREARM PLACEMENT OF EXTENDED DWELL CATHETERS: A COMPARATIVE EVALUATION OF BLOOD SAMPLING AND FUNCTIONALITY

site that is more suitable for cannulation. The site of insertion will be recorded and pertinent information will be collected similar to other enrollments.

The research team also will document practitioner details, the time of EDC placement, number of attempts, need for a rescue inserter, the vein that was cannulated, catheter to vein ratio, and the indication for EDC placement. Data will be collected from the electronic medical record and includes: age, gender, BMI, vital signs, relevant past medical history for difficult vascular access, and number, type, and site of previous vascular access devices during the current admission. The medication administration record will be queried for all medications given through each catheter. Specific attention will be given to vesicants listed in Appendix A. All upper extremity venous doppler imaging reports will be reviewed for thrombosis.

Follow-up Assessment

Investigators will perform a follow-up on the catheters daily while hospitalized. If qualified staff is not available, chart review will be performed on the first day staff returns back to the hospital. At each follow-up interval, the researcher notes the time of evaluation and assesses for blood sampling and functionality. At our institution, midlines and central lines can only be accessed for blood draws with a physician order. These instances are tracked in the medical record and will be recorded. The hospital policy for blood sampling follows Lippincott procedures for central venous access catheter blood sampling available at procedures.lww.com. If the qualified staff is able to aspirate blood from the catheter, blood sampling is considered intact. This sampling should be followed immediately by a 5-10 cc flush of saline to ensure no blood is visible in the tubing system. If blood does not readily aspirate, the line is flushed with 10 cc of saline and blood draw is re-attempted. If the catheter is unable to aspirate blood, the date and time of the failure of blood sampling is recorded. The presence or absence of blood within the lumen proximal to the hub is noted for occlusion for all VADs that cannot aspirate blood. After accessing the catheter, researchers are expected to flush and clean the catheter hub per institutional protocol for care and maintenance. All practitioners are given written instructions on this protocol. General functionality is also recorded if the VAD flushes with 5 ml of normal saline without resistance after the blood draw attempt. If the catheter cannot be flushed, the date and time of failure are recorded. If the catheter is identified to have failed prior to the follow-up assessment the date and time of failure and the reason for failure is obtained from chart review. If the patient is discharged prior to the time of follow-up assessment then the time of discharge is documented and the IV is presumed functional until time of discharge unless otherwise noted in the chart.

UPPER ARM VS. FOREARM PLACEMENT OF EXTENDED DWELL CATHETERS: A COMPARATIVE EVALUATION OF BLOOD SAMPLING AND FUNCTIONALITY

Sample Size and Statistical Analysis

The sample size for the proposed work is based on the first aim since the other aims will use the same samples. We determined the sample size for the proposed study based on the assumption that upper extremity catheters have successful blood sampling 50% of the time and clinically acceptable practice of 75% success applies to the experimental arm. If there is a true difference in favor of the experimental group of 25%, then 48 patients are required to be 95% sure that the upper limit of a one-sided 95% confidence interval (or equivalently a 90% two-sided confidence interval) will exclude a difference in favor of the control or upper arm group of more than 20%. Considering dropout rate and early discharge, we doubled the sample size to 96 patients. When evaluating volumes of midline catheters placed at our institution, this is a feasible number of patients to recruit over 4-6 months.

Initial analyses will include descriptive statistics for all outcomes using means, standard deviations, and ranges for continuous measures, and frequencies and percentages for categorical measures. We will compare demographic and other potential confounding variables between arms using either Pearson's chi-square test (dichotomous variables such as gender) or a two-sample t-test (continuous variables such as age), as appropriate. Aims will be assessed using survival analysis with Kaplan-Meier curves, Pearson's chi-squared test, and logistic regression.

Site

William Beaumont Hospital, Royal Oak (RO) campus is a 1,100 bed major academic and referral center with Level 1 adult trauma and Level 2 pediatric trauma status. A major teaching facility, Beaumont, Royal Oak has 55 residency and fellowship programs with 454 residents and fellows. Beaumont is the exclusive clinical partner for the Oakland University William Beaumont School of Medicine. The Beaumont Research Institute was established more than 30 year ago at Royal Oak and offers research support services to clinical investigators.

Principal Investigator

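### The primary comparison does not use ED versus inpatient entry as a stratum or covariate: still valid, but it may forgo a small gain in precision

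*Combined protocol and SAP*

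**What the plan says.** Study Population and Eligibility sets different entry rules by setting. For the ED: "Eligible ED patients include 1. 18 years and older 2. Difficult vascular access and anticipated hospital admission", where difficult access means no visible or palpable upper-extremity veins. For inpatients the rule is "Consult to VAT for vascular access device placement", a need for peripheral access, and adult age. The same section describes VAT consults as covering prolonged need, difficult access or both. It also describes ED physicians and nurses on one side and the VAT on the other, and Practitioner Participation/Training allows both groups to place study catheters.

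Under Initial Assessment, staff "will perform concealed immediate assignment by following a block scheme". No stratification factor is named. The variables listed there include practitioner details and the indication for placement, but not entry setting.

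Sample Size and Statistical Analysis names Kaplan-Meier curves, Pearson's chi-squared test and logistic regression for the aims, with no stratum or covariate. Study Design adds: "Exploratory secondary and adjusted multivariable analyses will also be conducted". No covariates are listed for those models.

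**The concern.** Entry setting is known for every patient before randomisation, and it could plausibly relate to the primary outcome. Vein quality, the inserter and the length of stay still to come may all affect whether a catheter fails to aspirate during hospitalisation, and the plan counts early discharge among its reasons for doubling the sample.

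If setting does predict failure, an unstratified comparison leaves the between-setting variation in the interval that decides non-inferiority. Precision matters here because the protocol's own hypothesis is that sampling is similar in the two sites, whereas the sample size assumes a large advantage for the forearm. The exploratory adjusted models do not fill the gap, because a covariate chosen after the data are seen cannot carry the non-inferiority decision.

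**Working it through.** **Inputs from the plan** (Sample Size and Statistical Analysis). Control: "upper extremity catheters have successful blood sampling 50% of the time". Experimental: "clinically acceptable practice of 75% success applies to the experimental arm". The interval "will exclude a difference in favor of the control or upper arm group of more than 20" per cent, one-sided 95%, with 95% assurance. The stated requirement is 48 patients, doubled to 96 (48 per arm).

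**Reproducing the plan's figure.** Per arm, n = (0.50×0.50 + 0.75×0.25) × (1.645 + 1.645)² / (0.25 + 0.20)² = 0.4375 × 10.82 / 0.2025 = 23.4. This rounds up to 24 per arm, 48 in total, and doubling gives 96. The plan's number reproduces.

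**Power if the sites are truly equal** (50% in both arms). With 48 per arm, SE = √(0.50/48) = 0.102. Power = Φ(0.20/0.102 − 1.645) = 62.4%. With 24 per arm it is 39.8%.

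**Effect of stratifying by setting.** Let q be the ED share and d the gap in success rate between settings. Stratification removes 2q(1−q)d² from the numerator of the risk-difference variance. The documents give neither q nor d, so I assume q from 0.2 to 0.5 and d from 10 to 30 points.

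| | q = 0.2, d = 0.10 | q = 0.5, d = 0.30 |
|---|---|---|
| 2q(1−q)d² | 0.0032 | 0.0450 |
| Share of 0.4375 removed | 0.7% | 10.3% |
| SE reduction, 50% v 75% | 0.4% | 5.3% |
| Required n per arm (from 24) | 24 | 21 |
| Power at 24 per arm, 50% v 75% (from 95.4%) | 95.5% | 97.0% |
| Power at 48 per arm, 50% v 50% (from 62.4%) | 62.6% | 65.9% |

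If d = 0, nothing is removed.

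**Chance imbalance.** With 48 per arm, the SD of the between-arm difference in ED share is √(2q(1−q)/48), or 8 to 10 points. An imbalance of 10 points or more has a probability of about 22% to 33%. The estimate shifts by d times the imbalance, so the variance of the shift is 2q(1−q)d²/48, which is exactly the term that stratification removes. For q = 0.5 and d = 0.30, the shift has SD 0.0306 and variance 0.00094. The unadjusted variance at 50% in both arms is 0.50/48 = 0.0104. The ratio is 9%, equal to 0.045/0.50. Imbalance and lost precision are one quantity.

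**Simulation** (40,000 runs per scenario, 48 per arm, q = 0.3 and 0.5, d = 0 to 0.30).
- At the 20-point margin, the one-sided error was 4.6% to 4.9% for the unstratified Wald bound and 5.0% to 5.4% for a Mantel-Haenszel bound with a simple large-sample variance.
- With equal arms, q = 0.5 and d = 0.30, the empirical SD fell from 0.1022 to 0.0978, that is 1 − 0.0978/0.1022 = 4.3%. The formula gives 1 − √(1 − 0.09) = 4.6%.
- At d = 0.10 and q = 0.5 the SD was essentially unchanged (0.1019 and 0.1020). At d = 0 it rose slightly (0.1020 to 0.1026).

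**The case against.** The strongest reply is that nothing goes wrong without the change. The unadjusted interval already contains the variance due to setting, randomisation protects against bias, the error rate holds, and the sample size stands. All of that is correct.

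Next, no passage shows that setting predicts aspiration failure. The populations overlap, since VAT consults include difficult-access patients. All patients receive the same catheter under ultrasound guidance from credentialed inserters, and ED patients must be expected to be admitted. This also stands, and it is why the gain is conditional. The difference in remaining stay is plausible but not documented.

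Third, the plan already foresees logistic regression, adjusted models and a comparison of potential confounders between arms. This stands in part: adjustment is planned, but not for the primary bound and with no covariates named. Logistic regression also yields an odds ratio, not a bound against a 20-point difference in proportions.

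Finally, the change is not free of drawbacks. With an assumed 20% ED share and 24 evaluable per arm, the ED stratum would hold about 0.2 × 24 ≈ 5 patients per arm.

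**Conclusion.** The point holds as a minor efficiency gain that the plan could take. The primary comparison as specified makes no use of entry setting. Over the assumed ranges, stratifying lowers the standard error by 0.4% to 5.3%, and raises power with equal arms and 48 per arm from 62.4% to between 62.6% and 65.9%. The upper end needs an even split and a 30-point gap. With a 10-point gap the gain is negligible, and if setting is not prognostic there is none.

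A reader might infer that the primary result would be biased, or that its error rate would be inflated. The design does not support this: allocation is randomised, and the simulated error stays just under 5%. A reader might also count chance imbalance as a harm on top of lost precision, but the two are the same variance. Nor do the documents support calling setting a strong predictor, since they give no success rate by setting. The stated sample size is unaffected.

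**What to change.** - Add entry setting (ED or inpatient) to the variables recorded at enrolment. If enrolment is complete, derive it from enrolment or medical records without reference to outcome.
- Before outcomes are compared by arm, state in the SAP that the one-sided 95% non-inferiority bound comes from a risk difference stratified by setting, for example Mantel-Haenszel. Name the variance or interval method, because the simple large-sample version ran slightly above 5% in simulation.
- Report the unadjusted risk difference as a sensitivity analysis.
- If a time-to-event test is used, make it a setting-stratified log-rank test rather than drawing separate Kaplan-Meier curves by setting, which could be very sparse.
- List the covariates for the exploratory adjusted models.

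The cost is one data field and a short SAP addition. No extra patients are needed and the randomisation need not change. The main drawback is that one stratum may be small if few ED patients enrol.

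### Emergency department and inpatient enrolments differ in entry criteria and inserters, yet no stratum or setting term is named; prespecifying setting would recover a little precision at almost no cost

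*Combined protocol and SAP*

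**What the plan says.** Study Population and Eligibility sets two entry routes. For inpatients the criteria, besides adult age, are "Consult to VAT for vascular access device placement 2. Patient requires peripheral access"; difficult access is not required. For the ED the text is "Eligible ED patients include 1. 18 years and older 2. Difficult vascular access and anticipated hospital admission", with difficult access defined by the absence of visible or palpable veins.

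The inserters also fall into two groups. Practitioner Participation/Training makes "Advanced Practice Providers (APP) within the VAT and ED practitioners proficient in ultrasound-guided vascular access" eligible to place study catheters, and Study Population and Eligibility adds "In the emergency department (ED), several physicians and nurses are competent in the procedure".

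Initial Assessment allocates patients "in a ratio of 1:1 via a computergenerated randomization schedule" and continues: "Research staff at the Department of Biostatistics will perform concealed immediate assignment by following a block scheme". Neither a block size nor a stratification factor is given.

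Sample Size and Statistical Analysis lists Kaplan-Meier curves, Pearson's chi-squared test and logistic regression for the aims, without naming setting or any other covariate. Study Design describes the adjusted multivariable analyses as exploratory. The data list in Initial Assessment includes practitioner details, time of placement and indication, but not enrolment setting as such.

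**The concern.** Setting may carry several things that bear on whether blood can still be drawn: vein quality (the access criterion differs), inserter group, and perhaps remaining time under observation. The last could matter because the Aim 1 event is a failure to aspirate at any follow-up during the stay, with no fixed time point, so a longer remaining stay gives more chances to fail. That ED patients have more of their stay ahead of them is plausible, but the documents do not say so.

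Unstratified blocks balance the arm totals, not the arms within each setting. If setting predicts the outcome, an unadjusted comparison leaves between-setting variation in the error term. What is at stake is the width of the interval set against the 20-point margin. That width matters most if the arms are truly similar, which is the protocol's own hypothesis for blood sampling.

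**Working it through.** **Inputs from the documents** (Sample Size and Statistical Analysis; Study Design). Control success is 50%: "upper extremity catheters have successful blood sampling 50% of the time". Experimental success is 75%, the margin is 20 points, and the interval is one-sided 95% (two-sided 90%). I read the stated 95% assurance as 95% power. The size is 48 patients, doubled to 96 for dropout and early discharge, with 48 per arm recruited.

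**Inputs assumed** (not in the documents). ED share *s* = 20-50%. Gap in success between settings *d* = 10-30 points.

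**1. The plan's own figure.** Per arm, n = (1.645 + 1.645)² × (0.50×0.50 + 0.75×0.25) / (0.25 + 0.20)² = 10.82 × 0.4375 / 0.2025 = 23.4, so 24 per arm and 48 in total. Doubling gives 96. The stated figure reproduces.

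**2. Chance imbalance in ED share.** Treating the ED counts in the two arms as independent binomials (a simplification of blocked allocation), the SD of the difference in share is √(2s(1−s)/n). At n = 48 this is √(0.32/48) = 8.2 points for s = 20% and √(0.50/48) = 10.2 points for s = 50%. Exact enumeration for s = 30% to 50% gives:

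| Evaluable per arm | P(at least 15 points) | P(at least 20 points) |
|---|---|---|
| 48 | 9-13% | 3-5% |
| 24 | 27-31% | 16-19% |

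**3. Effect on the primary difference.** The shift equals the imbalance times *d*. Its SD at n = 48 runs from 8.2 × 0.10 = 0.8 points to 10.2 × 0.30 = 3.1 points. In simulation the 95th percentile of its absolute size was 1.7-6.2 points. The standard error of the difference is 9.5 points under 50% v 75% (√(0.4375/48)) and 10.2 points with both arms at 50% (√(0.50/48)). The mean error in simulation was about zero.

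**4. Variance recovered by adjusting.** The proportion of variance due to setting is 2s(1−s)d² divided by the sum of the two arm variances.
- Both arms at 50%: 2×0.16×0.01/0.50 = 0.6% at the low end (s = 20%, d = 10) and 2×0.25×0.09/0.50 = 9% at the high end (s = 50%, d = 30).
- 50% v 75%: the same numerators over 0.4375 give 0.7% and 10.3%.

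The range is therefore roughly 1-10%.

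**5. Power at N = 96, all evaluable.**
- Planned 50% v 75%: Φ(0.45/0.0955 − 1.645) = Φ(3.07) = 99.9%. Simulation gave at least 99.8% with or without adjustment.
- Both arms at 50%, unadjusted: Φ(0.20/0.1021 − 1.645) = Φ(0.315) = 62%.
- Both arms at 50%, 9% less variance: SE = 0.1021 × √0.91 = 0.0974, so Φ(0.20/0.0974 − 1.645) = 66%. Across the assumed range, simulation put adjusted power at about 62-68%.

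**6. What does the work.** In simulations with both arms at 50%, stratified lists with an unadjusted analysis gave 62-63%. Adjustment gave 63-67% with or without stratified lists.

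**7. If only 24 per arm are evaluable.** Under 50% v 75%, power is Φ(0.45/0.1350 − 1.645) = 95%. With both arms at 50%, simulated power was about 44% unadjusted and 42-45% adjusted, so adjustment brings no dependable power gain at that size.

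**The case against.** The strongest reply is that unstratified blocks in a single-site trial of 96 are valid and stratifying is a preference. That stands as to validity. Four readings go further than the documents allow:

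- **That the trial is biased, or that imbalance is a separate threat to the margin.** Random allocation makes the imbalance average zero, and the unadjusted 90% interval already covers it.
- **That a sizeable imbalance is likely.** At the planned 48 per arm, a gap of at least 15 points has a 9-13% chance. Even at 24 per arm the chance is below one in three.
- **That separate lists would remove imbalance and narrow the interval.** Lists balance randomised patients, whereas the planned doubling anticipates heavy loss afterwards. Starting from 96 patients split perfectly by setting, random loss of half still leaves an imbalance of at least 15 points in 12-16% of simulated trials (ED share 30-50%). The narrower interval comes from the adjustment.
- **That the protocol rules out strata.** It is silent. A single unstratified list is the natural reading of the singular wording, but only an inference.

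It is also fair to say that the settings overlap. VAT consults include difficult-access patients, all inserters are ultrasound-trained, and device training precedes recruitment. Practitioner details, vessel depth and diameter, and prior devices are recorded, so setting or its mechanisms could be partly reconstructed. Exploratory adjusted analyses are planned as well. What remains is that no covariate is named and the primary comparison does not use setting.

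**Conclusion.** The point holds as a minor, low-cost improvement, not as an error. It changes neither the sample size nor the power at the planned rates. Its value lies in the case where the arms are similar: roughly 1-10% less variance, and up to about 6 points of power at N = 96 from a base of about 62%. Both figures depend on an assumed ED share of 20-50% and an assumed setting gap of 10-30 points. If setting does not predict blood sampling, there is nothing to recover. Prespecification has a further benefit that does not depend on these figures: it settles whether to adjust for setting before any imbalance is seen.

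**What to change.** In Initial Assessment, state the block size, generate two permuted-block lists (ED and inpatient) with separate envelopes, and record setting at enrolment. If strata already exist, one sentence should say so.

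In Sample Size and Statistical Analysis, prespecify the Aim 1 comparison as a Mantel-Haenszel risk difference stratified by setting, with its 90% interval set against the 20-point margin. Stratify the Aim 2 time-to-event comparison by setting.

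If only one change is made, it should be the analysis term together with the recorded field, since these supply the precision; the lists add balance among randomised patients. The cost is a second list and envelope set, one more recorded field and a sentence or two of text, with no extra patients.
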